Study design		Using a traditional "3+3" dose-escalation design, subjects will be sequentially assigned to one of three dose groups (2.8×10^{10} units, 1.4×10^{11} units, and 7.0×10^{11} units per dose, once daily, with continuous intranasal instillation for 4 days). Each dose group will include 3 subjects, who will be enrolled one by one. The exploration of the next dose can only proceed if no dose-limiting toxicity (DLT) is observed in the 3 subjects. If 1 out of the 3 subjects experiences DLT, an additional 3 subjects will be enrolled in the same dose group; the exploration of the next dose can only move forward if no DLT is observed in these newly added 3 subjects. A minimum of 6 and a maximum of 18 subjects will be recruited during the dose exploration phase. Patients will receive other standard medical treatments in accordance with the recommendations in the 2022 Chinese Guidelines for Secondary Prevention of Ischemic Stroke and Transient Ischemic Attack , including antiplatelet drugs or anticoagulants, antihypertensive drugs, lipid-lowering drugs, and glucose-lowering drugs.
Outcome Measures	Primary Outcome Measure	Dose-Limiting Toxicity (DLT) Related to hUC-MSC-sEV-001 Includes: (1) Grade 3-4 severe adverse events occurring on day 14 (+-2), graded according to Common Terminology Criteria for Adverse Events (CTCAE) V5.0; (2) NIHSS score increase of ≥ 4 from baseline on day 14 (+-2); NIHSS score assessed by a professional rehabilitation physician;(3) Symptomatic intracranial hemorrhage occurring on day 14 (+-2); detected via CT scan and patient symptom presentation.
	Secondary Outcome Measures:	Serious adverse events related to the investigational drug within 90 (+-7) days. Distribution of Modified Rankin Scale (mRS) Scores within 90 (+-7) days. Barthel Index within 90 (± 7) days. Five-level, five-dimensional EuroQol (EQ-5D-5L) . Proportion of Modified Rankin Scale (mRS) Scores of 0-2 within 90 (+-7) days. All-cause mortality at 90 (+-7) days. Changes in infarct volume at 14 (+-2) days compared to baseline. Change from Baseline in National Institutes of Health Stroke Scale (NIHSS) Score.
Follow-up duration		Baseline (0~1 day), 7 (± 1) days, 14 (± 2) days, 90 (± 7) days
Sample size		6-18 subjects need to be included.

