Single-center, prospective, dose-escalation clinical trial.

(2) Trial Administration Strategy

A traditional "3+3" dose-escalation design will be adopted. Subjects will be sequentially assigned to one of three dose groups (2×10^{10} units, 1×10^{11} units, 5×10^{11} units per administration, once daily for 4 consecutive days via intranasal instillation). Each dose group initially enrolls 3 subjects, with sequential enrollment (i.e., the next subject is enrolled only after the previous subject completes the 14-day DLT observation period).

- If no DLT is observed in 3 subjects of a dose group, the study proceeds to the next higher dose level.

- If 1 out of 3 subjects experiences DLT, an additional 3 subjects are enrolled in the same dose group. If no DLT is observed in the additional 3 subjects, the study proceeds to the next higher dose level; if ≥ 1 additional subject experiences DLT, the current dose level is defined as the maximum tolerated dose (MTD), and dose escalation is terminated.
- A total of 6 to 18 subjects will be recruited during the dose-escalation phase.

(3) Study Suspension or Early Termination

The study will be suspended or terminated early if any of the following occurs:

- Violation of the *Good Clinical Practice (GCP)* or the *Administrative Measures for Stem Cell Clinical Research (Trial)*;
- Emergence of new safety or efficacy data on MSC-sEVs indicating that the trial poses a serious risk to patient safety or is clearly ineffective;
- Failure to enroll subjects as scheduled for 3 consecutive months;
- Major protocol deviations that affect the validity of study data;
- Request for termination by the sponsor or regulatory authorities.

2. Subject Selection Criteria

(1) Inclusion Criteria

- Confirmed diagnosis of acute ischemic stroke (in accordance with the *Chinese Guidelines for the Diagnosis and Treatment of Acute Ischemic Stroke (2023)*);
- Aged 18-70 years, regardless of gender;
- Anterior circulation occlusion (internal carotid artery, middle cerebral artery M1/M2 segment) confirmed by CTA or MRA;
- mRS score of 0-1 before the current stroke episode (indicating no or minimal disability prior to the index event);
- ASPECTS ≥ 6 on non-contrast computed tomography (NCCT) or diffusion-weighted imaging (DWI) after stroke onset (indicating a small to moderate infarct volume);
- NIHSS score ≥ 6 at screening (indicating moderate to severe neurological deficit);

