- **Specification:** 2.0 mL/bottle; concentrations corresponding to the three dose groups: 1×10^{10} particles/mL, 5×10^{10} particles/mL, and 2.5×10^{11} particles/mL
- **Storage Conditions:** $-80^{\circ}\text{C} \pm 10^{\circ}\text{C}$ (ultra-low temperature refrigerator), protected from light; no repeated freezing-thawing
- **Pretreatment Agent:** Hyaluronidase for injection (150 U per nostril), used to improve nasal mucosa permeability
- **Administration Route:** Intranasal instillation (bilateral nostrils)

(2) Treatment Protocol

1. **Baseline Assessment:** Complete all screening assessments (laboratory tests, imaging, neurological scales) before the first dose.
2. **Nasal Mucosa Pretreatment:** Administer 150 U hyaluronidase (dissolved in 0.5 mL normal saline) to each nostril via a nasal dropper, and wait 15 minutes for absorption.
3. **Study Drug Administration:** Instill hUC-MSC-sEV-001 into bilateral nostrils using a dedicated dropper:
 - Low dose: 1 mL per nostril (total dose: 2×10^{10} particles);
 - Medium dose: 1 mL per nostril (total dose: 1×10^{11} particles);
 - High dose: 2 mL per nostril (total dose: 5×10^{11} particles).
4. **Administration Frequency:** Once daily for 4 consecutive days (Day 0: enrollment

day, Day 1, Day 2, Day 3).

5. **Concomitant Standard Treatment:** All subjects receive standard medical treatment for ischemic stroke in accordance with guidelines, including:

- Antiplatelet therapy (e.g., aspirin 100 mg/day, clopidogrel 75 mg/day);
- Antihypertensive therapy (target blood pressure: <140/90 mmHg for non-diabetic subjects, <130/80 mmHg for diabetic subjects);
- Lipid-lowering therapy (target low-density lipoprotein cholesterol [LDL-C]: <1.8 mmol/L);
- Glycemic control (target fasting blood glucose: 4.4-7.0 mmol/L for diabetic subjects).

(3) Rehabilitation Therapy

All subjects receive standardized rehabilitation therapy starting from Day 1 after enrollment, including:

- Manual therapy (e.g., joint mobilization, muscle strength training);
- Occupational therapy (e.g., activities of daily living training, fine motor skill training);
- Speech therapy (if applicable for subjects with aphasia);
- Physical therapy (e.g., gait training, balance training) as needed.

The type and duration of rehabilitation therapy are documented in the "Rehabilitation Therapy Record Form" in the CRF.

(4) Precautions During Intervention

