2. Efficacy Assessments:

- Neurological scales: NIHSS, mRS, MBI, EQ-5D-5L;
- Infarct volume measurement (DWI) and CTP parameter analysis.

3. Documentation: Record combined medications, rehabilitation therapy, and schedule the Day 90 visit.

Fourth Visit (Day 90 ± 7)

1. Safety Assessments:

- Vital signs measurement;
- Laboratory tests: CBC, clinical chemistry, coagulation function, serum electrolytes, infectious disease screening, tumor markers, urinalysis, pregnancy test (if applicable);
- Imaging examinations: Chest X-ray, 12-lead ECG, DWI, FLAIR, CTA/CTP;
- Final AE follow-up (until 30 days after the last dose).

2. Efficacy Assessments:

- Neurological scales: NIHSS, mRS, MBI, EQ-5D-5L;
- Final infarct volume measurement and CTP parameter analysis.

3. Study Completion: Confirm completion of all assessments, and document any protocol deviations.

Items/Visits	Baseline (Day 0)	Day 7 (±1)	Day 14 (±2)	Day 90 (±7)
Sign Informed Consent Form	●			
Review Inclusion/Exclusion Criteria	●			
Collect Demographic & Clinical Data	●	●	●	●
Vital Signs	●	●	●	●
Urine Pregnancy Test	●			●
Hematology (CBC) *	●	●	●	●
Clinical Chemistry (Liver/Kidney Function, Glucose, Lipids) *	●	●	●	●
Coagulation Function (PT, INR, APTT, FIB)	●		●	●
Serum Electrolytes	●		●	●
Infectious Disease Screening (8 Items)	●		●	●
Tumor Markers (AFP, CA199, CEA) *	●		●	●
Urinalysis *	●	●	●	●

Items/Visits	Baseline (Day 0)	Day 7 (±1)	Day 14 (±2)	Day 90 (±7)
Chest X-ray	•		•	
12-Lead ECG	•		•	•
Cerebral Imaging (CT/MRI/CTA/CTP)	•	•	•	•
Neurological Scales (NIHSS, mRS)	•	•	•	•
Modified Barthel Index (MBI)	•		•	•
EQ-5D-5L Score	•		•	•
Record Adverse Events	•	•	•	•
Record Concomitant Medications	•	•	•	•
Record Rehabilitation Therapy	•	•	•	•

7. Regulations for Packaging, Acceptance, Storage, Distribution, and Recovery of Study MSC-sEV Preparations

(1) Packaging of Study MSC-sEV Preparations

- **Primary Packaging:** Sterile glass vials (2.0 mL) with rubber stoppers and aluminum caps, labeled with the study drug name, batch number, dose level, expiration date, storage conditions, and "For Clinical Trial Use Only".
- **Secondary Packaging:** Individual cartons containing one vial of study drug and one vial of hyaluronidase, with a leaflet describing the administration method.
- **Tertiary Packaging:** Insulated containers with dry ice for transportation, labeled with "Biological

Product", "Keep Frozen (-80°C)", and the sponsor's contact information.

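### The high-dose instruction delivers twice the stated high dose, and the synopsis lists three dose levels that are each 1.4 times those in the body

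*Protocol*

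**What the plan says.** Section 3(1), Trial Drug, gives the product as "2.0 mL/bottle; concentrations corresponding to the three dose groups: 1×10^{10} particles/mL, 5×10^{10} particles/mL, and 2.5×10^{11} particles/mL". Section 3(2), Treatment Protocol, then gives a volume and a total for each level, instilled into both nostrils. The first line is "Low dose: 1 mL per nostril (total dose: 2×10^{10} particles". The medium dose is also 1 mL per nostril, for a total of 1×10¹¹. The last line is "High dose: 2 mL per nostril (total dose: 5×10^{11} particles".

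Section 1(2), Trial Administration Strategy, names the same totals as the escalation levels: "2×10^{10} units, 1×10^{11} units, 5×10^{11} units per administration". The Study design row of the synopsis names a different set: "2.8×10^{10} units, 1.4×10^{11} units, and 7.0×10^{11} units per dose". Both describe the same once-daily, four-day intranasal regimen under the same 3+3 scheme.

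Section 7(1), on packaging, describes "Individual cartons containing one vial of study drug and one vial of hyaluronidase". No part of the protocol says which set of levels governs or tells staff to use more than one vial for a dose.

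**The concern.** Dose level is the experimental variable in this trial. Dose-limiting toxicity (DLT) is the primary outcome, escalation proceeds by dose level, and the maximum tolerated dose (MTD) is defined as a dose level. If one line of the dosing instruction gives a different amount from the total beside it, and the synopsis gives a third figure, it is unclear what the top cohort will receive and what its DLT count describes.

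A site that follows the written volume gives top-level subjects twice the named dose, and section 3(4) allows no dose reduction. The protocol's own rules add to the problem. Section 2(5) treats a wrong dose as a severe violation that removes a subject from the efficacy set. Section 2(7) makes an unapproved dose modification that invalidates the results a ground for stopping the study. Neither rule can be applied while the intended dose is ambiguous.

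**Working it through.** **Inputs.** Concentrations and the 2.0 mL vial come from section 3(1). Volumes per nostril and stated totals come from section 3(2). There are two nostrils. The synopsis levels come from its Study design row.

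**Formula.** Total dose = concentration (particles/mL) × volume per nostril (mL) × 2.

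| Level | Calculation | Result | Stated in 3(2) | Result ÷ stated |
|---|---|---|---|---|
| Low | 1×10¹⁰ × 1 × 2 | 2×10¹⁰ | 2×10¹⁰ | 1.0 |
| Medium | 5×10¹⁰ × 1 × 2 | 1×10¹¹ | 1×10¹¹ | 1.0 |
| High | 2.5×10¹¹ × 2 × 2 | 1×10¹² | 5×10¹¹ | 2.0 |

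Two of the three rows reproduce exactly, which confirms the formula and isolates the high-dose row.

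**Alternative reading.** Taking 2 mL as the total for both nostrils gives 2.5×10¹¹ × 2 = 5×10¹¹, the stated figure. That contradicts the words of the line, and the low and medium rows work only if their volumes are per nostril.

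**Vial.** The high-dose instruction needs 2 × 2 = 4 mL, which is two 2.0 mL vials. One vial holds 2.0 × 2.5×10¹¹ = 5×10¹¹ particles.

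**Escalation steps.** Section 1(2): 1×10¹¹ ÷ 2×10¹⁰ = 5 and 5×10¹¹ ÷ 1×10¹¹ = 5. Synopsis: 1.4×10¹¹ ÷ 2.8×10¹⁰ = 5 and 7.0×10¹¹ ÷ 1.4×10¹¹ = 5. As instructed, the second step is 1×10¹² ÷ 1×10¹¹ = 10.

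**Course total at the high level.** 4 × 1×10¹² = 4×10¹² as instructed, against 4 × 5×10¹¹ = 2×10¹² as stated.

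**Synopsis against body.** 2.8×10¹⁰ ÷ 2×10¹⁰ = 1.4×10¹¹ ÷ 1×10¹¹ = 7.0×10¹¹ ÷ 5×10¹¹ = 1.4. A constant ratio at all three levels does not look like a misread character. Both places count in the same unit, so a change of unit does not explain it. The dose as instructed is 1×10¹² ÷ 7×10¹¹ = 1.43 times the synopsis top level.

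**Could the listed product give the synopsis levels?** 2.8×10¹⁰ ÷ 1×10¹⁰ = 1.4×10¹¹ ÷ 5×10¹⁰ = 7.0×10¹¹ ÷ 2.5×10¹¹ = 2.8 mL per dose, which is more than one vial. At 1 mL per nostril the product would have to be 1.4×10¹⁰, 7×10¹⁰ and 3.5×10¹¹ particles/mL, and none of these is listed.

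**The case against.** The body of the protocol points fairly clearly to 5×10¹¹. The stated total, the level in section 1(2), the content of one high-strength vial and the one-vial carton all agree, and only the volume is out of line. On that view this is a single slip, 2 mL written for 1 mL per nostril. Giving 1×10¹² would mean opening a second vial for a dose whose printed total equals one.

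There are also controls that could expose the error: dose and deviation records after each administration (section 7(2)), full source data verification (section 10(1)) and monthly inventory checks (section 12(2)). Subjects enter one at a time, each after the previous subject's 14-day observation period, so extra vial use could surface with the first high-dose subject.

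Much of this stands. A slip in the volume is the likeliest explanation, and 1×10¹² is implied by the instruction, not printed as a level. The 2.8 mL figure is an inference too, because the synopsis gives no concentration or volume. The protocol reports no toxicity by dose, so nothing here rests on the top level being the most toxic.

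These points do not remove the fault. Nothing forbids a second vial, the controls act mainly after a dose has been given, and the written instruction is still to instil 4 mL. Correcting the volume would also leave the 1.4-fold conflict between synopsis and body, which affects every level from the first subject onwards.

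**Conclusion.** The concern holds, as two separate faults. First, the high-dose instruction gives 1×10¹² particles, 2.0 times its own stated total. If a site follows it, the last escalation step is 10-fold and not 5-fold, and DLTs and any MTD at that level would be attached to the wrong dose. Second, the synopsis and the body differ by a factor of 1.4 at all three levels, with nothing to reconcile them.

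The first result assumes that the listed concentrations belong to the three groups in order, as section 3(1) states, and that per nostril means what it says. The second needs no assumption beyond comparing two current passages. The synopsis row on the experimental drug also mentions a dose, but it is illegible in the copy reviewed and is not relied on. The document cannot show which levels the sponsor intends. Because these are dosing instructions in an escalation trial, they must be corrected before anyone is treated.

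**What to change.** The sponsor should state which three levels are intended, then align the synopsis, section 1(2), the concentrations and vial size in section 3(1), the volumes in section 3(2) and the packaging in section 7(1). At each level, concentration × volume per nostril × 2 must equal the one stated total.

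- If 5×10¹¹ is intended, the simplest change is 1 mL per nostril at 2.5×10¹¹/mL: 2 mL, one vial. The alternative is 2 mL per nostril at 5×10¹¹ ÷ 4 = 1.25×10¹¹/mL: 4 mL, two vials. Either way the synopsis levels need correcting.
- If the synopsis levels are intended, sections 1(2) and 3 must change, with new concentrations or volumes and a stated number of vials per dose.

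The number of vials per dose should be written into section 3(2). DLT and MTD results should be labelled by the particle count actually delivered. The cost is protocol wording and a check against the dosing and pharmacy instructions, with no additional patients or procedures.
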